7.6.3 Sensitivity Analyses

In the event that rescue medication is used, a supplementary MMRM model will be applied to the primary endpoint dataset that excludes data collected after the initiation of the rescue medication using the mITT population. This model will be parameterized in the same manner as will be used for the primary analysis of this endpoint.

In addition, to assess the robustness of the MMRM analyses performed under the MAR assumption, and given the long half-life of LX9211, PMMs with copy reference-based imputation methods will be applied to both datasets (with and without data collected after the initiation of the rescue medication) using the mITT population. Methods will be adopted to estimate for both non-monotone and monotone missing data patterns. Imputations for the non-monotone missing data pattern will be the initial step. The imputation algorithm based on Monte Carlo Markov Chain methodology will be used assuming a MAR mechanism for the missing data; 100 imputations will be used. Then multiple imputations will be performed to assign the response variable at consecutive study weeks in a sequential manner for the monotone missing data pattern. For this chain-based method, control-based imputation will be applied so that there is no direct use of observed data from the LX9211 treatment group in estimating the imputation model. The method is derived such that it builds its imputation only on the placebo group data. The imputed datasets will be combined by use of Rubin's rule and analyzed using an analysis of covariance (ANCOVA) model fitted with the fixed effects of treatment, the

randomization stratum of the Baseline pain severity (moderate, severe), and the continuous fixed covariate of Baseline score. The ANCOVA analysis will be performed at Week 6 only. Summary statistics from applying the ANCOVA model across the multiple imputed datasets will be combined to obtain an overall estimate of the treatment group differences.

Another sensitivity analysis will be performed for the weekly sleep score, which is the average of the daily score by week through Week 6. The baseline is the Week 2 sleep score from the Run-in period. The change from baseline to Week 6 will be analyzed by using a similar MMRM method as the primary endpoint.

In the case there are patients with PK anomalies, eg, LX9211 randomized patients with $C_{trough}=0$ during double-blind phase, sensitivity analyses will be performed excluding these patients from the primary analysis model for the primary endpoint at Week 6.

7.6.4 Subgroup Analysis

The primary endpoint will be analyzed using the mITT population for the following subgroups:

- Baseline pain severity based on the actual stratum, moderate or severe
- Sex, male or female
- Baseline PHN drug use, yes or no
- Subjects who experience the 5 specific TEAEs, yes or no

Baseline PHN drug use subgroup is defined as those who took concomitant PHN medications including the following: pregabalin, gabapentin, duloxetine, amitriptyline, venlafaxine, desvenlafaxine, valproic acid.

The 5 specific TEAEs refer to the AEs: dizziness, headache, nausea, somnolence, and balance disorder, which usually occur more frequently than other AEs.

The same MMRM covariates used for the primary endpoint analysis will be used for the subgroup analyses except that for the Baseline pain severity subgroup analysis, the randomization stratum of Baseline pain severity (moderate, severe) will not be included as a covariate. A forest plot of the LS Means difference and 95% CI for the comparison of LX9211 versus placebo with the change from Baseline scores will be presented for all subgroups.

All subgroup analyses will be exploratory.

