5.1 Overall Study Design

This is a Phase 2, multicenter, randomized, double-blind, placebo-controlled, parallel-group study in patients with PHN.

[figure not shown]
Scheduled study visits in the clinic will occur during Screening; at the initiation of the 2-week single-blind placebo Run-in Period; on Day 1 (Baseline), and during Weeks 2, 4, and 6 of the double-blind Treatment Period, and Week 11 of the single-blind Safety Follow-up Period.

Male and female patients, ≥ 18 years of age, inclusive, with prior herpes zoster skin rash and PHN pain persisting for ≥ 3 months after healing of the herpes zoster skin rash, and who meet all inclusion and no exclusion criteria are eligible for enrollment.

Eligible patients may continue use 1 medication prescribed for PHN including pregabalin, gabapentin, and tricyclic antidepressant (TCA) medications, as long as they have been at stable doses for ≥ 1 month prior to Screening and are willing to maintain their doses for the duration of the study. Patients taking more than 1 permitted concomitant medication for the treatment of PHN and unable to washout all but 1 of these treatments for the duration of the study are not eligible. Use of any new medications, prescribed or over-the-counter (OTC), for treatment of PHN pain is not permitted during the course of the study. Use of any opioid medications for the management of PHN within the 2 months prior to Screening is not permitted.

The treatment schema is summarized in [Figure 5.1-1](#).

Figure 5.1–1 Treatment Schema

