8. For non-opioid medications patient uses and is unwilling/unable to discontinue use of prohibited medications and therapies, (eg, benzodiazepines, dextromethorphan, herbal medications, mexiletine HCl, adenosine, topical analgesics including lidocaine and capsaicin), applied to the same area of the body affected by PHN pain, nerve blocks, acupuncture, or other medications indicated for neuropathic pain. A patient using any of these interventions for neuropathic pain must discontinue the medication ≥ 1 month prior to starting the Screening Period and for the duration of the study. **Note:** This exclusion criterion does not include analgesics that are not specifically prescribed for treatment of neuropathic pain (eg, nonsteroidal anti-inflammatory drugs [NSAIDs], aspirin, acetaminophen). In addition, patients who are prescribed antidepressants for a mental health disorder are eligible to participate as long as they do not meet Exclusion Criteria 2-3.
9. A positive urine drug test for drugs of abuse including cannabinoids. **Note:** Cannabidiol (CBD), if used for mood or sleep, is acceptable. If used for PHN it would be allowed if it is the only concomitant medication being taken for PHN. If not, the only medication being taken for PHN, it should be withdrawn ≥ 1 month prior to Screening.
10. Patient has hepatic impairment at Screening, defined as any of the following: aspartate aminotransferase (AST) $> 2X$ upper limit of the normal reference range (ULN), alanine aminotransferase (ALT) $> 2X$ ULN, serum total bilirubin (TB) $> 2X$ ULN. **Note:** If it is the opinion of the Investigator and the Medical Monitor that an increase in bilirubin is due to Gilbert's syndrome, then the patient may participate.
11. Patient has abnormal kidney function test (estimated glomerular filtration rate [eGFR] < 60 mL/min as calculated using the Cockcroft-Gault equation) at Screening or renal dysfunction requiring hemodialysis
12. Patient has any of the following medical conditions or disorders: epilepsy or seizure disorder requiring treatment with antiepileptic drugs
13. Presence of clinically significant physical examination (PE) findings other than PHN, or laboratory or ECG findings that in the opinion of the Investigator, Medical Monitor,

and/or the Sponsor, may interfere with any aspect of study conduct or interpretation of results including:

- a. any clinically significant abnormal heart rate or rhythm
 - b. other ECG abnormalities that are clinically relevant

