7.2.2 Concomitant Medication

All medications and other treatments ongoing or taken from the start of the Screening Period, through the end of the Safety Follow-up Period of the study will be recorded on the eCRF as concomitant medication. This includes any ongoing medications for the treatment patients' PHN (ie, gabapentin, pregabalin, and tricyclic antidepressant medications).

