7.4.2 Prior and Concomitant Medications

Medications received prior to or concomitantly with study drug will be coded using the World Health Organization (WHO) Drug Dictionary (Version B3 Sep2020 or a later version if updated during the study]), Anatomical Therapeutic Chemical (ATC) Classification codes.

Prior medications and concomitant medications are defined as follows:

- Prior medications are those taken prior to the first dose date of double-blind treatment, and with a stop date before first dose date of double-blind treatment.
- Concomitant medications are those with a start date on or after the first dose date of double-blind treatment, or those with a start date before the first dose date of double-blind treatment and a stop date on or after the first dose date of double-blind treatment.

If a medication cannot be classified as “prior” or “concomitant” after applying imputation rules for missing/incomplete dates, it will be classified as concomitant.

Prior medications, concomitant medications taken during double-blind Treatment Period (excluding prohibited and rescue concomitant medications), prohibited concomitant medications taken during double-blind Treatment Period, and concomitant medications started during Safety Follow-up Period (those medications starting after the last dose of double-blind study drug and through the end of the patient's Safety Follow-up Period) will be summarized separately by treatment group and overall for the mITT population.

The number and percentage of patients using each medication will be displayed together with the number and percentage of patients using at least 1 medication within each therapeutic class (ATC-Level 2), chemical subgroup (ATC-Level 4), and generic term.

The percentage of patients who need rescue medication during the double-blind Treatment Period will be summarized descriptively by treatment group and overall for the mITT population.

Prior medications, concomitant medications and rescue concomitant medications will be listed separately.

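### The SAP's Baseline PHN drug use subgroup has no Day 1 cut-off, so a drug started after randomisation can make a patient a baseline user, and its drug list does not line up with the protocol's permitted PHN medications

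*SAP*

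**What the plan says.** SAP 7.6.4 plans the primary endpoint by Baseline PHN drug use (yes or no) and defines the yes group as "those who took concomitant PHN medications including the following: pregabalin, gabapentin, duloxetine, amitriptyline, venlafaxine, desvenlafaxine, valproic acid". It gives no date rule, no rule on indication and no source field.

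SAP 7.4.2 says what concomitant means: "Concomitant medications are those with a start date on or after the first dose date of double-blind treatment". A second limb adds drugs started earlier and still being taken on or after that date. The section also plans a separate summary of concomitant medications started during Safety Follow-up, and it sends medications that cannot be classified to the concomitant group. The protocol's own definition (7.2.2) is wider: "All medications and other treatments ongoing or taken from the start of the Screening Period", through to the end of Safety Follow-up.

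On what is permitted for PHN, the protocol speaks in several places:
- Section 5.1: "Eligible patients may continue use 1 medication prescribed for PHN including pregabalin, gabapentin, and tricyclic antidepressant (TCA) medications". SAP 2.2 repeats this in substance.
- Section 7.2.2, on ongoing PHN medication: "ie, gabapentin, pregabalin, and tricyclic antidepressant medications".
- Exclusion 9, on cannabidiol: "If used for PHN it would be allowed if it is the only concomitant medication being taken for PHN".
- Exclusion 8, among the prohibited therapies: "nerve blocks, acupuncture, or other medications indicated for neuropathic pain".
- The note to Exclusion 8: "patients who are prescribed antidepressants for a mental health disorder are eligible to participate as long as they do not meet Exclusion Criteria 2-3".

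Protocol 7.3 bars new PHN medication during the study. Baseline PHN drug use also appears as a row in the baseline table (SAP 7.4). SAP 7.7.2 tabulates five specific TEAEs by PHN drug use, with the number of patients in each category as the denominator.

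**The concern.** A baseline subgroup should be fixed by what was true before the first double-blind dose. If later events can change membership, the comparison within each subgroup is no longer protected by randomisation. The direction of the problem is easy to see here: a patient who adds a PHN drug during the study probably does so because pain control is poor. Membership would then depend partly on the outcome being analysed.

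The drug list raises a separate issue of classification. The sponsor treats background PHN medication as relevant to efficacy, since taking more than one such drug (Exclusion 7) is among the entry violations that remove a patient from the per-protocol population (SAP 5.3.1). If permitted background drugs are left out of the definition, or drugs taken for another reason are let in, the two subgroups no longer separate patients with and without background PHN treatment. In the TEAE table the denominators move as well, so the reported percentages change.

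**Working it through.** **1. Plan figures.** No figure in either document depends on this definition. The stated power of 82.27% reproduces with 37 per group, a difference of 0.68, SD 1 and two-sided alpha 0.05 (noncentral t: 82.27%). It does not change with the subgroup rule.

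**2. The lists side by side.**

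| Drug | Protocol 5.1, 6.2, 7.2.2 | SAP 7.6.4 |
|---|---|---|
| Pregabalin, gabapentin | Named as permitted | Named |
| Tricyclics | Permitted as a class | Amitriptyline only |
| Cannabidiol for PHN | Allowed as the sole PHN drug | Not named |
| Duloxetine, venlafaxine, desvenlafaxine, valproic acid | Not named as permitted | Named |

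**3. The rule applied to patient types.** Reading A takes the list as closed and matches by drug name. Reading B takes it as open and limits it to drugs taken for PHN. Both use concomitant as SAP 7.4.2 defines it. The last column is status at Day 1. The fourth row assumes that a listed antidepressant was prescribed for a mental health disorder; the documents do not say so drug by drug.

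| Patient | A | B | Day 1 status |
|---|---|---|---|
| Amitriptyline for PHN, ongoing at Day 1 | Yes | Yes | Yes |
| Another tricyclic for PHN, ongoing at Day 1 | No | Yes | Yes |
| Cannabidiol as sole PHN drug, ongoing at Day 1 | No | Yes | Yes |
| Listed antidepressant for a mental health disorder, ongoing at Day 1 | Yes | No | No |
| Gabapentin for PHN started on Day 20 | Yes | Yes | No |
| Gabapentin for PHN started in Safety Follow-up | Yes | Yes | No |

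The list errors (rows 2 to 4) appear under Reading A and vanish under Reading B. The timing errors (rows 5 and 6) appear under both. In row 6 the drug starts after the Week 6 endpoint, yet it sorts the patient for the Week 6 analysis.

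**4. Illustration of size, on assumed values only.** Let q be the true share of users, se the share of users filed yes, and sp the share of non-users filed no. For misfiling unrelated to outcome, the share of the true user versus non-user contrast that is kept is PPV + NPV − 1, where PPV = q·se / [q·se + (1−q)(1−sp)] and NPV = (1−q)·sp / [(1−q)·sp + q(1−se)].

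Example with q = 0.5 and se = sp = 0.9: PPV = 0.45/0.50 = 0.90, NPV = 0.45/0.50 = 0.90, kept = 0.80.

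| se, sp | Contrast kept, q from 0.3 to 0.7 |
|---|---|
| 0.9, 1.0 | 81–96% |
| 0.9, 0.9 | 75–80% |
| 0.7, 0.8 | 42–51% |

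For scale, 10% misfiled in each direction in a trial of 74 is 0.1 × 74 = 7.4 patients.

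**5. Precision of the subgroup estimates.** With SD 1, 37 per arm and no dropout, the 95% half-width for a treatment difference is 1.96·√(2/n per arm). A subgroup holding 30% of patients has 11.1 per arm and a half-width of 0.83. At 50% it is 18.5 and 0.64; at 70% it is 25.9 and 0.54. The planned difference before the dropout adjustment is 0.8.

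**The case against.** The strongest reply is that the wording can be read sensibly throughout. The word including, in both SAP 7.6.4 and protocol 5.1, can introduce examples, so another tricyclic or cannabidiol taken for PHN would still count. The phrase PHN medications can carry an indication condition, so an antidepressant taken for mood would not count. The protocol is itself uneven: open wording in 5.1, closed wording in 7.2.2, a prohibition in Exclusion 8. The variable is labelled Baseline, and the second limb of the concomitant definition is the natural one for it. New PHN drugs are barred, so late starters are deviators and probably few. Prohibited medications are summarised separately, and patients who take them during double-blind treatment leave the per-protocol set. The analysis is exploratory, with no interaction test planned.

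Most of this stands against the list. A reader might infer that the SAP contradicts the protocol and that users and non-users are in fact being swapped. The documents do not support that: misfiling needs a closed list matched by name, and neither is stated. It is equally unstated that the list is open or limited by indication, so two programmers could derive different flags.

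Less of it stands against the timing. The label signals the intention, but the definition under it uses a term that SAP 7.4.2 has defined to include later starts. Per-protocol exclusion does not help, because the subgroup is run on the mITT population.

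**Conclusion.** The timing defect holds. As written, the rule lets a start after the first double-blind dose, even in Safety Follow-up, set membership of a baseline subgroup. The mismatch between the lists also holds as a matter of text, but its consequence is conditional: patients can be misfiled in either direction if the list is closed and matched by name.

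The size cannot be determined. The documents give no count of users, of late starters or of antidepressant users, and do not say how the list was compiled; if it reflects drugs actually recorded, few patients may be affected. A reader might take the illustration as showing that a fifth or more of the user versus non-user contrast is lost. It does not show that: the error rates are assumed, and at a sensitivity of 0.9 with no false users 81–96% is kept. The formula also assumes misfiling unrelated to outcome. Membership driven by response could bias the estimates in either direction, and the formula does not measure that.

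The effect is confined to an exploratory subgroup with wide intervals, a baseline table row and a TEAE table. The last two are included on the inference that they use the same flag, since neither SAP 7.4 nor 7.7.2 defines its own. The primary analysis, sample size and interim decision are untouched.

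**What to change.** Replace the definition in SAP 7.6.4 with one rule. Baseline PHN drug use is yes if any medication taken for PHN, including any tricyclic or cannabidiol, was started before the first double-blind dose and was ongoing at that dose; otherwise it is no. State that the named drugs are examples. State how missing or partial start dates are handled, because SAP 7.4.2 sends unclassifiable medications to concomitant by default. Use the same flag, by cross-reference, in SAP 7.4 and 7.7.2. This concerns classification only and leaves the rules on permitted medication as they are.

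The cost is a short SAP edit and one derivation, to be settled before unblinding. Medications are already recorded on the eCRF. The documents do not show an indication field; if there is none, indication can be confirmed in a blinded medication review, and SAP 5.3.1 already has the Medical Monitor reviewing blinded medication listings.

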7.6.5 Other Efficacy Analysis

Descriptive statistics for the all efficacy endpoints will be presented by treatment group and by study visit/week across double-blind Treatment Period and single-

blind Safety Follow-up period. Data from all study visits, scheduled and unscheduled, will be listed.

7.6.5.1 Change from Baseline to Week 6 in the NPSI

The NPSI, a 12-item questionnaire, assesses the different components of neuropathic pain syndromes (ie, spontaneous ongoing and paroxysmal pain, evoked pain, paresthesia/dysesthesia). 10-items related to different pain descriptors (eg, burning, squeezing, electric-shock, stabbing, tingling) allows assessment of the different dimensions of neuropathic pain and 2 items on frequency and duration of pain.

The total intensity score and the 5 subscores (burning spontaneous pain, pressing spontaneous pain, paroxysmal pain, evoked pain, and paresthesia/dysesthesia) will be calculated as:

- Total intensity score: $Q1+Q2+Q3+Q5+Q6+Q8+Q9+Q10+Q11+Q12$
- (Superficial spontaneous) Burning pain: $Q1$
- (Deep spontaneous) Pressing pain: $(Q2+Q3)/2$
- Paroxysmal pain: $(Q5+Q6)/2$
- Evoked pain: $(Q8+Q9+Q10)/3$
- Paresthesia/dysesthesia: $(Q11+Q12)/2$

Baseline will be the data collected on Day 1 at Visit 3. The change from Baseline to Week 6 in total intensity score and the 5 subscores will be summarized using standard descriptive statistics and the treatment effect will be evaluated using an ANCOVA model fitted for the fixed effects of treatment, the randomization stratum of Baseline pain severity (moderate, severe), and the continuous fixed covariate of Baseline score. The ANCOVA analysis will be performed at Week 6 only.

The adjusted mean change from Baseline to Week 6 for each treatment group and the 95% CIs will be estimated in the framework of this model, as well as the between-group differences (comparing LX9211 to placebo) and the 95% CIs for the difference.

Summarization of the inferential statistics will include the LS means, SE of the estimates, p-values, and 2-sided 95% CIs. These statistics will be provided for the within treatment group changes from Baseline and for the comparison of LX9211 versus placebo for the change from Baseline scores. Tabulation of the inferential results (CIs and p-values) will include the observed model findings.

7.6.5.2 Change of Question 5 of the ZBPI from Baseline to each post-Baseline visit

Baseline will be the data collected on Day 1 at Visit 3. For this endpoint, we will use the Question 5 of the ZBPI, collected at clinic visits and visit windows defined in

section 6.1.2. The values collected for each post-Baseline visit and the change from Baseline at post-Baseline visits will be summarized by visit (ie, Weeks 2, 4, and 6) and treatment group using standard descriptive statistics. The treatment effect will be evaluated using a similar MMRM method as specified for the primary efficacy analysis of change from Baseline to Week 6.

The change from Baseline values at post-Baseline visits will be calculated as the absolute difference between Baseline value and post-Baseline values, ie,

$$\text{Change from Baseline} = \text{post-Baseline value} - \text{Baseline value}$$

7.6.5.3 Proportion of patients with $\geq 30\%$ reduction from Baseline in ADPS, based on Question 5 of the ZBPI by week

Baseline and weekly ADPS scores will be based on the mean values as described in the primary efficacy analysis. Missing ADPS scores derivations at any week will be imputed as non-response. The frequency and percentages of patients with $\geq 30\%$ reduction in pain intensity from Baseline, based on Question 5 of ZBPI collected each evening on the e-diary, will be presented by Week and treatment group.

7.6.5.4 Proportion of patients with $\geq 50\%$ reduction from Baseline in ADPS, based on Question 5 of the ZBPI by week

Baseline and weekly ADPS scores will be based on the mean values as described in the primary efficacy analysis. Missing ADPS scores derivations at any week will be imputed as non-response. The frequency and percentages of patients with $\geq 50\%$ reduction in pain intensity from Baseline, based on Question 5 of ZBPI collected each evening on the e-diary, will be presented by Week and treatment group.

7.6.5.5 Cumulative distribution function of percent change in ADPS based on Question 5 of the ZBPI from Baseline to Week 6 comparing the LX9211 treatment group to placebo

Baseline and Week 6 ADPS scores will be based on the same mean values as derived for the primary endpoint. A descriptive plot of the cumulative distribution function of percent change from Baseline to Week 6 in ADPS based on Question 5 of the ZBPI collected each evening on the e-diary will be presented by treatment group.

$$\% \text{ change from Baseline to Week 6} = 100 * (\text{Week 6 value} - \text{Baseline value}) / \text{Baseline value.}$$

7.6.5.6 Cumulative distribution function of percent change in ADPS based on Question 5 of the ZBPI from Week 6 to Week 11 comparing the LX9211 treatment group to placebo

Week 6 and Week 11 ADPS scores will be based on the mean weekly values as described in the primary efficacy analysis. A descriptive plot of the cumulative distribution function of percent change from Week 6 to Week 11 in ADPS based on

Question 5 of the ZBPI collected each evening on the e-diary will be presented by treatment group. Where percent change from Week 6 to Week 11 will be defined as:

$$\% \text{ change from Week 6 to Week 11} = 100 * (\text{Week 11 value} - \text{Week 6 value}) / \text{Week 6 value}.$$

